- **Renal artery imaging** will be performed at the 6-month follow-up visit to assess if a renal artery stenosis is suspected. A renal duplex ultrasound (DUS) will be obtained at 6-months follow up and submitted to the DUS Core Laboratory. If the DUS is determined to be nondiagnostic a repeat DUS, a MRA, CT or angiogram will be performed (repeat imaging is to be completed within 30 days after confirmation of non-diagnostic imaging). If evidence of a clinically significant stenosis is indicated by the DUS or MRA/CT Core Laboratory, an angiogram must be obtained and submitted to the angiographic core laboratory.
  - If renal imaging is not obtained at the 6-month follow-up visit due to extenuating circumstances, renal imaging is required at the next scheduled study visit.
- **24-hour ABPM** will be conducted at the 3, 6, and 12-month follow-up visits post-procedure according to the guidelines in **Appendix 16.5**. A repeat ABPM will be required in the event of technical issues, failure to follow ABPM guidelines or if the minimum required number of daytime and nighttime readings is not obtained. If ABPM is repeated office blood pressure and drug testing (for 3-month follow up only) must be repeated on day the ABPM is applied.
  - Initiate medication re-Introduction for subjects with systolic OBP  $\geq 140$  mmHg at 3-month follow-up visit. Starting at the 3-month follow up after clinical assessment and a valid ABPM are completed.
- **Mortality assessment** will be completed by the investigational site when a subject cannot be reached after each of the protocol required follow-up visits.
- **Drug testing** (urine/blood) to ensure medications are no longer present in the subject's system. A urine sample will be collected, preferably using the subject's first morning urine. A blood sample will be collected at the time of the visit. Drug testing samples collected for subjects that screen fail after obtaining the sample, must not be sent to the core lab for analysis.

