Appropriate cardiac enzyme data (respecting top-down hierarchy):

a) CK greater than or equal to 2\* URL confirmed by:

- CKMB > 1\*URL or
- in the absence of CKMB: Troponin > 1\*URL or

b) in the absence of CK:

- CKMB > 3\*URL
- In the absence of CK and CKMB: Troponin > 3\*URL
- In the absence of CK, CKMB and Troponin, clinical decision based upon clinical scenario

**New renal artery stenosis:** Greater than 70% renal artery stenosis confirmed by analysis of angiography by the core lab. If core lab analyses are unavailable, site reported analysis may be used. The date of the event will be the date of confirmatory angiography.

**Renal artery dissection:** Creation of a false lumen between the layers of the artery requiring intervention.

**Renal artery perforation:** Puncture creating a hole in the vessel wall requiring intervention.

**Renal artery reintervention:** Interventional procedure performed on the renal artery following completion of the renal denervation procedure and removal of the guide catheter.

**Significant embolic event:** Sudden obstruction of a blood vessel by debris (i.e., blood clot, plaques, fat, bacterial mass, cancer cells, or air bubbles) resulting in end-organ damage. Examples include:

- Kidney/bowel Infarct: necrosis (cell death) of an area of tissue in all or part of the organ due to cessation of the blood supply due to stenosis or occlusion
- Lower extremity ulceration: a non-healing lesion on a body surface (i.e., skin, mucous membrane)
- Gangrene: necrosis of tissue usually resulting from deficient or absent blood supply
- Doubling of serum creatinine confirmed by at least two measurements over 21 days apart
- DOES NOT INCLUDE MI OR STROKE WHICH ARE ADJUDICATED SEPARATELY

**Stroke:** Sudden onset of vertigo, numbness, dysphasia, weakness, visual field defects, dysarthria, or other focal neurological deficits due to vascular defects in the brain such as hemorrhage, embolism, thrombosis, or rupturing aneurysm, that persists more than 24 hours.

**Vascular Complications:** Complications that require surgical repair, interventional procedure (not including manual compression), thrombin injection, or blood transfusion (requiring more than 2 units of packed red blood cells within any 24-hour period during the first 7 days post-procedure); possible vascular complications are as follows:

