7.7. Evaluation of Objectives

7.7.1. Safety Objectives

The following safety endpoints will be evaluated:

- Major Adverse Events (MAE), defined as a composite of the following event at 1 month post-procedure (6 months for renal artery stenosis):
 - All-cause mortality
 - End-stage renal disease (ESRD)
 - Significant embolic event resulting in end-organ damage
 - Renal artery perforation requiring intervention
 - Renal artery dissection requiring intervention
 - Vascular complications
 - Hospitalization for hypertensive crisis not related to confirmed non-adherence with medications or the protocol
 - New renal artery stenosis >70%, confirmed by angiography and as determined by the angiographic core lab at 6 months follow-up
- Composite safety endpoint, defined as a composite of the following event at 3, 6 and 12-month post-procedure:
 - All-cause mortality
 - End-stage renal disease (ESRD)
 - Significant embolic event resulting in end-organ damage
 - Renal artery perforation requiring intervention
 - Renal artery dissection requiring intervention
 - Vascular complications
 - Hospitalization for hypertensive crisis not related to confirmed non-adherence with medications or the protocol

This document is electronically controlled. Printed copies are considered uncontrolled.

Confidential

- New renal artery stenosis >70%, (For the composite safety endpoint at 3 and 6 months, use RAS at 6 months, which confirmed by angiography and as determined by the angiographic core lab at 6 months follow-up. For the composite safety endpoint at 12 months use RAS available at 12 months)
- Myocardial infarction
- Stroke
- Renal artery re-intervention
- Major bleeding according to TIMI definition (i.e. intracranial hemorrhage, $\geq 5\text{g/dl}$ decrease in hemoglobin concentration a $\geq 15\%$ absolute decrease in hematocrit, or death due to bleeding within 7 days of the procedure)
- Increase in serum creatinine $>50\%$ from SV2 (not CEC adjudicated)

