All the safety endpoints except "Increase in serum creatinine $>50\%$ from SV2" will be adjudicated by the Clinical Events Committee (CEC). The following algorithm will be used to evaluate the safety event rates: The denominator will include all subjects who either had a CEC adjudicated event prior to the time of interest (180 days for 6 months events, for example), or had last contact date that is beyond the lower window of the follow up (166 days for 6 month events, for example). The numerator will include all subjects who had CEC adjudicated events up to the time of interest (180 days for 6 months events, for example).

The safety endpoints will be summarized using counts and percentages, and no comparison group will be used for the safety analysis. These analyses will be performed for the ITT population defined in 7.1.3.1.

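### The SAP stops the 6-month safety numerator at day 180, although 6-month renal imaging may run to day 194 and a stenosis takes the later angiogram date; as written, such a stenosis can go uncounted.

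*SAP*

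**What the plan says.** **Event-rate algorithm (SAP 7.7.1).** One algorithm serves all the safety event rates. For the numerator: "The numerator will include all subjects who had CEC adjudicated events up to the time of interest (180 days for 6 months events". A subject without an event enters the denominator if he or she "had last contact date that is beyond the lower window of the follow up (166 days for 6 month events". Both day figures are given as examples, and stenosis is not mentioned in the algorithm.

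**Endpoint list (SAP 7.7.1).** The MAE composite is set at 1 month, with 6 months for renal artery stenosis. For the later composites the list says "For the composite safety endpoint at 3 and 6 months, use RAS at 6 months" and "For the composite safety endpoint at 12 months use RAS available at 12 months". It attaches no day limit to either.

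**Imaging (Protocol 9.1.6 and Table 3).** Duplex ultrasound is the first-line test at the 6-month visit, whose window is ±14 days. The angiogram comes second: "If evidence of a clinically significant stenosis is indicated by the DUS or MRA/CT Core Laboratory, an angiogram must be obtained". No time limit is set for it. After a nondiagnostic study, "repeat imaging is to be completed within 30 days after confirmation of non-diagnostic imaging". If imaging is missed at 6 months, "renal imaging is required at the next scheduled study visit", which is the 12-month visit.

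**Event date (Protocol 16.4, new renal artery stenosis).** "The date of the event will be the date of confirmatory angiography".

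**The concern.** The 6-month imaging is there to look for stenosis. Its confirmation comes after the visit's first imaging, because a core laboratory must read that study before the angiogram is ordered, and the event then carries the angiogram date. A numerator that closes on the visit's target day will therefore tend to close before the confirmation is dated.

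The error can go only one way. A late-dated stenosis leaves the numerator, while the subject, with contact after day 166, remains in the denominator as event-free. The rates concerned are the 1-month MAE and the 3- and 6-month composites, since all three draw on 6-month stenosis.

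SAP section 8 has two programmers produce the tables independently. One could follow the endpoint list and the other the algorithm, and reach different 6-month rates from the same data. The choice between them might then be made with a known event in view.

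**Working it through.** **Inputs**
- Numerator limit for 6-month events: day 180 (SAP 7.7.1).
- 6-month visit: target day 180, ±14 days (Protocol Table 3; SAP Appendix II).
- Event date: day of the confirmatory angiogram (Protocol 16.4).
- Treated subjects: about 50 (SAP section 5).
- Delay from imaging to angiogram, and spread of visits within the window: not in the documents; assumed below.

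**Plan's own figure.** 180 − 14 = 166, the lower limit used in SAP 7.7.1. 180 + 14 = 194, the upper limit in Appendix II. Both reproduce.

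**Result that needs no assumption.** Imaging on day t with an angiogram d days later is counted only if t + d ≤ 180, that is, d ≤ 180 − t.
- t = 166: the angiogram must follow within 14 days.
- t = 180: it must be on the same day.
- t = 181 to 194: it is never counted. That is 14 of 29 permitted days (14/29 = 48%).
- d ≥ 15: no in-window visit yields a counted event, because 166 + 15 = 181.
- Nondiagnostic first study with the full 30 days used: the repeat falls on day 166 + 30 = 196 at the earliest, already past 180.

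**Share of confirmed stenoses dated after day 180, under assumed delay and visit spread**

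| Visit spread (assumed) | d = 0 | d = 7 | d = 14 | d ≥ 15 |
|---|---|---|---|---|
| Even over 29 days | 14/29 = 48% | 21/29 = 72% | 28/29 = 97% | 100% |
| Triangular, weight 15 − \|t − 180\|, sum 225 | 105/225 = 47% | 189/225 = 84% | 224/225 = 99.6% | 100% |
| Days 166–180 weight 2, later days weight 1, sum 44 | 14/44 = 32% | 28/44 = 64% | 42/44 = 95% | 100% |

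**Effect of one omission, as an illustration.** With 50 subjects, 1/50 = 2.0% (exact 95% CI 0.05% to 10.6%) becomes 0/50 = 0% (0% to 7.1%).

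**Same check at 12 months.** The SAP gives no 12-month day in the algorithm. If the target day 360 of Appendix II is used, the visit window is days 330 to 390, or 61 days, of which 30 fall after day 360 (30/61 = 49%). Imaging deferred to that visit meets the same limit, and no later composite can pick it up.

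**The case against.** The strongest reply is that the endpoint list in SAP 7.7.1 already treats stenosis as a special case. Stenosis found at 6 months can enter a 1-month or 3-month composite only if the ordinary day limits are set aside, so a literal application of the algorithm would empty that instruction of meaning. The list also ties stenosis to the 6-month follow-up, and the day-180 figure is only an example. For office pressure, ABPM and laboratory values the SAP uses an expanded 6-month window of days 136 to 270, so it does not generally equate 6 months with day 180.

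This is good evidence of intent, and it makes omission possible rather than certain. It does not settle the rule. A programmer can carry 6-month stenosis into the earlier composites and still define it by day 180, the only working definition of a 6-month event that the section offers. The expanded windows do not name imaging.

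Other points that stand:
- Safety is reported as counts and percentages, with no comparison group and no test.
- Most omitted events should appear in the 12-month composite, and subject listings are planned.
- Independent programming may expose the divergence before reporting. It would not say which reading is right.
- The CEC works under a separate charter (Protocol 12.1). Whether that charter assigns events to visits cannot be seen from these documents.

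A reader might infer that the plan will drop every stenosis found at 6 months, or that 32% to 100% of them will be lost. The documents support neither. The first ignores the endpoint list; the second depends on the literal reading and on assumed delays and visit spreads.

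**Conclusion.** The point holds as an unresolved conflict between two rules in SAP 7.7.1. Applied as written, the algorithm can omit a stenosis found by the 6-month imaging from three composites and score the subject as event-free. That imaging on 14 of the 29 permitted days can never produce a counted event follows from the stated dates alone; the larger shares rest on assumptions.

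The consequence is limited. No hypothesis, sample size or efficacy result is affected. The number of stenoses is unknown and may be zero, and each omission would move a rate by about 2 percentage points (1/50). It would be wrong to conclude that the reported safety rates will be understated: that requires at least one late-dated stenosis and the literal reading. The change is still worth making before analysis, because the possible error always favours the device and the remedy is very cheap.

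**What to change.** Add to SAP 7.7.1:

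> Renal artery stenosis is exempt from the day cut-offs: any confirmed >70% stenosis arising from the 6-month imaging work-up counts in the 1-month MAE and the 3-, 6- and 12-month composites whatever the angiogram date; stenosis first found on imaging deferred to the 12-month visit counts in the 12-month composite whatever the angiogram date.

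Moving the 6-month limit to day 194 would not be enough. It covers same-day angiograms, but imaging on day 194 with a 30-day delay gives day 224.

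Beside these rates, report the number of subjects with diagnostic renal imaging. A subject whose imaging was deferred or nondiagnostic can still sit in the 6-month denominator, and the count lets the reader see how many were actually examined. The denominator rule itself can stay.

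Cost: one sentence and one reported count, with no new data, visits or procedures.

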7.7.2. Efficacy Objectives

The following efficacy endpoints will be compared to the SPYRAL HTN-OFF MED efficacy endpoints using a propensity score stratified analysis at 3 months. The multiple sources of study patients in HTN-OFF MED study are shown in Table 1. At 6 months and 12 months, the endpoints will be analyzed within the SPYRAL DYSTAL study only.

- Change in systolic blood pressure (SBP) from baseline (SV2) to 3, 6, and 12 months postprocedure as measured by 24-hour ABPM.
- Change in office SBP from baseline (SV2) to 3, 6 and 12 months post-procedure.
- Change in diastolic blood pressure (DBP) from baseline (SV2) to 3, 6, and 12 months postprocedure as measured by 24-hour ABPM.
- Change in office DBP from baseline (SV2) to 3, 6, and 12 months post-procedure.
- Incidence of achieving target office SBP $<140\text{ mmHg}$ at 3, 6 and 12 months.

Table 1: Study Sources of Patients in HTN-OFF MED for Efficacy Endpoint Data (RDN arm only)

Study
SPYRAL HTN-OFF MED data (First 80 Subjects)
Randomized 1:1 to RDN:CONTROL
SPYRAL PIVOTAL – SPYRAL HTN-OFF MED Randomized 1:1 to RDN:CONTROL

This document is electronically controlled. Printed copies are considered uncontrolled.

Confidential

SPYRAL PIVOTAL – SPYRAL HTN-OFF MED
(Secondary Cohort)
Randomized 1:1 to RDN:CONTROL

7.7.2.1. Efficacy Objectives Evaluation at 3 Months

Since subjects in the two comparative groups were not directly randomized, a direct comparison may not be appropriate. The efficacy endpoints at 3-months will be compared to the RDN treated subjects from the SPYRAL HTN-OFF MED clinical study using propensity score stratification (subclassification) adjustment. A propensity score will be estimated for each patient from a multivariable logistic regression model, which is the probability that the patient is in DYSTAL cohort. In this model, the DYSTAL cohort (binary variable) is the outcome variable, and the following covariates will be considered as independent variables for propensity score analysis model: baseline Office SBP and DBP as well as the SBP and DBP measured by 24-hour ABPM (continuous), age (continuous), gender (dichotomous), BMI (continuous), diabetes (dichotomous).

The missing values in the covariates will be imputed first before the propensity score stratification. For continuous variables, the missing values will be imputed by CALL STREAMINIT(seed) and RAND('NORMAL', MU, S²), where MU denotes the sample mean of the specific continuous variable, S denotes the sample standard deviation. If the imputed value is above the maximum value of that variable, the maximum value will be used as the imputed value; if the imputed value is below the minimum value of the variable, the minimum value will be used as the imputed value. For binary categorical variables, the missing values will be imputed as RANBIN(seed, 1, p), where p denotes the observed proportion of the specific binary baseline variable in each arm. The seed will be set as 121919, applied for both continuous and binary variable imputations.

After propensity scores are estimated, the entire population will be divided into 5 strata using the quintiles of the ordered propensity scores, with approximate equal number of subjects from Dystal study cohort in each stratum. This will be done using PROC PSMATCH in SAS 9.4, specifying the option KEY=TREATED in STRATA statement to require that each stratum contain approximately equal number of subjects from Dystal cohort. The option STRATUMWGT=TOTAL in STRATA statement, which uses the proportional size (number of total units in the stratum divided by the total number of units) of the stratum, will provide the average treatment effect weight for each observation.

After stratification, analysis of covariance (ANCOVA) models adjusting for the baseline BP measurements will also be presented for each propensity score stratum to obtain the strata-specific treatment effect, which can be combined to yield an overall treatment effect (DYSTAL minus SPYRAL HTN-OFF MED RDN arm). The overall treatment effect together with two-sided 95% confidence interval will be calculated as follows:

$$(\mu_D - \mu_R) \pm 1.96 \times \text{SE}(\mu_D - \mu_R),$$

where $\mu_D - \mu_R$ is the weighted mean of overall treatment effect given by

This document is electronically controlled. Printed copies are considered uncontrolled.

Confidential

$$\mu_D - \mu_R = \sum_{k=1}^5 w_k (\mu_{kD} - \mu_{kR}),$$

with k the number of stratum ($k = 1, 2, 3, 4, 5$), and w_k as the weight for k^{th} stratum defined by

$$w_k = \frac{N_{kD} + N_{kR}}{\sum_{k=1}^5 (N_{kD} + N_{kR})}$$

Additionally, $\mu_{kD} - \mu_{kR}$ is the mean of treatment effect in k^{th} stratum from an ANCOVA adjusted model, and $SE(\mu_D - \mu_R)$ is the weighted standard error of overall treatment effect

$$SE(\mu_D - \mu_R) = \sqrt{\sum_{k=1}^5 w_k^2 * SE^2(\mu_{kD} - \mu_{kR})},$$

where $SE(\mu_{kD} - \mu_{kR})$ is the standard error of treatment effect in k^{th} stratum.

The ITT population will be the primary analysis population, and secondary analyses will be performed on the modified ITT and per protocol populations in 7.1.3.2 and 7.1.3.3.

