In order to test the hypothesis in the SPYRAL PIVOTAL - SPYRAL HTN-OFF MED study that renal denervation decreases blood pressure and is safe when studied in the absence of antihypertensive medications, study subjects were randomized to the Denervation or Control group in a 1:1 fashion. In addition to subjects being blinded to their randomization assignment, site personnel involved in the measurement of office blood pressure were also blinded to study subjects' randomization assignment through the primary endpoint to prevent potential bias of results. Subjects were studied in the absence of antihypertensive medications to assess the impact of renal denervation on systolic blood pressure in the absence of medication.

Study enrollment was stopped for efficacy after the first interim analysis in February 2020. Data from the initial 80 patients with three months follow up from the SPYRAL HTN-OFF MED study was combined with data from the initial 251 patients with three months follow up from the SPYRAL PIVOTAL-SPYRAL HTN-OFF MED study and was presented at ACC World Congress of Cardiology in March 2020. Concurrently, an article presenting the data was published in *The Lancet*. A brief summary of the SPYRAL PIVOTAL-SPYRAL HTN-OFF MED data is provided below.

The primary endpoint, change in 24-h blood pressure at three months, was compared between groups. Drug surveillance was done to ensure patient compliance with absence of antihypertensive medication. The primary analysis was done in the intention-to-treat population. Safety events were assessed to three months.

From June 25, 2015, to Oct 15, 2019, 1519 patients were enrolled, of whom 1188 were excluded because they did not meet inclusion criteria. 166 were randomly assigned to renal denervation and 165 to the sham procedure (80 were included in the pilot and 251 in Pivotal).

There were no major safety events reported at one month. There was one major safety event in each treatment group up to three months (one admission to hospital for hypertensive crisis or emergency in the renal denervation group and one new stroke in the sham procedure group), and neither was attributed to the device or trial procedures.

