### 8.3. Inclusion Criteria

1. Individual is  $\geq 20$  and  $\leq 80$  years old at time of enrollment (consent).
2. Individual has an office systolic blood pressure (SBP)  $\geq 150$  mmHg and  $< 180$  mmHg and an office diastolic blood pressure (DBP)  $\geq 90$  mmHg measured at Screening Visit 2, according to the guidelines in **Appendix 16.5**.
3. Individual has a valid 24-hour ABPM average SBP  $\geq 140$  mmHg and  $< 170$  mmHg measured at Screening Visit 2, according to guidelines in **Appendix 16.5**.  
ABPM is considered valid if the number of successful daytime readings captured is  $\geq 21$  and the number of successful nighttime readings captured  $\geq 12$ .
4. Individual agrees to have all study procedures performed, and is competent and willing to provide written, informed consent to participate in this clinical study.
5. Individual is willing to discontinue current antihypertensive medications at Screening Visit 1 through the 3-month post-procedure visit.

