7.1.3. Analysis Sets

7.1.3.1. Intention-To-Treat (ITT) Population

All enrolled subjects are included in the intention-to-treat population. Subjects who meet the antihypertensive medication escape criteria (confirmed OSBP \geq 180 mmHg or safety reasons) will be analyzed using Last Observation Carried Forward (LOCF) for their blood pressure measurements, safety outcomes, and office and ambulatory blood pressure outcomes from procedure up to 3 months will be presented for this population.

The LOCF will be determined for the subjects who meets all following criteria:

1. Include any office or ambulatory BP values performed \leq escape date.
2. Include any office or ambulatory BP values performed \geq 30 days post procedure date.
3. Use most recent remaining greater than 30 days post-procedure measurement up to 3 months, including unscheduled BP measurements.

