7.3. Handling of Missing Data and Dropouts

No imputation of missing data will be performed.

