11.1. Appendix I: Imputation of AE Onset or Anti-Hypertensive Medication Start Dates

The table below specifies how to input missing dates for AE onset or anti-hypertensive medication start dates:

Valid Portion	Missing Portion	Imputed Value for Missing Portion
Month, Year	Day	Set Day = first day of that month and year, then set the day = later of (new onset date, informed consent date).
Year	Day, Month	Set date = later of (January 1st of that year, informed consent date).
None	Day, Month, Year	Informed consent date

This document is electronically controlled. Printed copies are considered uncontrolled.

Confidential

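### SAP 7.7.2.1 passes the variance S² to a SAS normal generator that takes a standard deviation, so imputed propensity covariates are drawn too wide and often land on the observed minimum or maximum

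*SAP*

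**What the plan says.** The 3-month comparison with the SPYRAL HTN-OFF MED denervation arm rests on propensity score strata. SAP 7.7.2.1 fills missing covariates before the score is estimated. For the continuous ones (office and 24-hour SBP and DBP, age, BMI) it prescribes a SAS call rather than a distribution in words: values are "imputed by CALL STREAMINIT(seed) and RAND('NORMAL', MU, S²"), where MU is the sample mean and "S denotes the sample standard deviation". A range rule follows: "If the imputed value is above the maximum value of that variable, the maximum value will be used as the imputed value", with the mirror-image rule at the minimum. The seed is fixed at 121919. No other section restates or corrects the call.

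SAP 7.3, the general section on missing data, says: "No imputation of missing data will be performed". Besides the covariates in 7.7.2.1, two other places do impute. In 7.1.3.1, subjects who meet the escape criteria "will be analyzed using Last Observation Carried Forward (LOCF) for their blood pressure measurements". Appendix I opens with "The table below specifies how to input missing dates for AE onset or anti-hypertensive medication start dates". Protocol 13.7 leaves room for specified exceptions to its no-imputation rule; SAP 7.3 does not.

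**The concern.** The call and the definition of S do not fit together. If S is the SD, S² is the variance, and the SAS function reads its third argument as an SD. The documents do not state this last fact; it is a property of the software they name. For any covariate with S above 1, which is certain for mmHg, years and kg/m², the draw is then S times too wide.

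The range rule hides the error. Draws far outside the data become the smallest or largest observed value, so nothing implausible shows in the output. A safeguard that should rarely act would produce a large share of the imputed values. A subject placed at an extreme gets a distorted propensity score and may fall in the wrong stratum, and the stratum cut-points can move for others. Apart from the within-stratum ANCOVA on baseline blood pressure, these strata are the only adjustment for the lack of randomisation.

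**Working it through.** **Inputs from the documents.** The call, the definition of S and the range rule (SAP 7.7.2.1). About 50 treated DYSTAL subjects (protocol 13.3). For the comparator, "166 were randomly assigned to renal denervation and 165 to the sham procedure" (protocol 3.1). The pool is therefore 50 + 166 = 216; the secondary cohort in SAP Table 1 has no stated size and is left out. The 24-hour SBP eligibility range is 140 to below 170 mmHg (protocol 8.3).

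**Assumed.** All SDs, the BMI range and the missing rates. The plan has no figure of its own that depends on this rule, so there is nothing to reproduce first.

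**Step 1: share of draws reset, range fixed.** With the mean at mid-range and half-range h, P(reset) = 2 × (1 − Φ(h / SD)). SD = S² as written; SD = S as presumably meant.

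| Covariate | S | h | With S² | With S |
|---|---|---|---|---|
| BMI | 4 | 10 | 2(1 − Φ(10/16)) = 53% | 2(1 − Φ(2.5)) = 1.2% |
| BMI | 4 | 12 | 2(1 − Φ(12/16)) = 45% | 2(1 − Φ(3)) = 0.3% |
| BMI | 4 | 16 | 2(1 − Φ(16/16)) = 32% | below 0.1% |
| BMI | 5 | 12.5 | 2(1 − Φ(12.5/25)) = 62% | 2(1 − Φ(2.5)) = 1.2% |
| BMI | 5 | 15 | 2(1 − Φ(15/25)) = 55% | 2(1 − Φ(3)) = 0.3% |
| BMI | 5 | 16 | 2(1 − Φ(16/25)) = 52% | below 0.3% |
| 24-h SBP | 7.5 | 15 | 2(1 − Φ(15/56.25)) = 79% | 2(1 − Φ(2)) = 5% |
| 24-h SBP | 8 | 15 | 2(1 − Φ(15/64)) = 81% | 2(1 − Φ(1.875)) = 6% |

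With an off-centre BMI (mean 31, range 18 to 48), the shares are 35%, 55% and 68% for S = 4, 5 and 6, against 0.1%, 0.5% and 1.7%. After resetting, the SD of the imputed values is still 11.0, 12.5 and 13.3, against 4.0, 5.0 and 5.9.

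**Step 2: observed range simulated.** With the minimum and maximum taken from simulated samples of 216 (normal BMI, mean 30), the share reset is 49%, 58% and 64% for S = 4, 5 and 6, against about 1%. A lognormal BMI gives 49%, 58% and 64%, against 1.3 to 1.8%.

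**Step 3: which covariates can be missing.** Office SBP and DBP at Screening Visit 2 and age are eligibility conditions, and so is 24-hour SBP ("Individual has a valid 24-hour ABPM average SBP", protocol 8.3). The 24-hour DBP comes from the same recording. BMI is neither an eligibility condition nor named in the visit schedule. The 24-hour SBP rows above therefore show how the rule behaves, not where it will bite.

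**Step 4: number of subjects.** Suppose 1 to 5% of 216 lack BMI, that is 2 to 11 subjects. Lowest case: 216 × 0.01 × 0.317 = 0.7. Highest case: 216 × 0.05 × 0.617 = 6.7. So about 1 to 7 subjects would get an extreme value. With S, the highest case is 216 × 0.05 × 0.018 = 0.19.

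**Step 5: effect on the estimate.** The 7.7.2.1 analysis was simulated with 50 + 166 subjects, eight covariates, five strata on DYSTAL quintiles, total-size weights and ANCOVA. Each setting had 400 replicates, with the same random draws scaled by S or by S². Assumed: BMI SD 5, outcome SD about 10.5, BMI missing completely at random in 2, 5 or 11 subjects, and a BMI effect on blood pressure change of 0 or 0.3 mmHg per kg/m².

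- Median absolute shift in the overall estimate: 0.08 to 0.22 mmHg; 95th percentile 0.43 to 0.80.
- Mean shift: at most 0.06 mmHg. Standard error of the estimate: about 1.86 mmHg.
- Subjects whose stratum changes: about 10 to 29, because cut-points move.
- Root mean square deviation from the complete-data estimate: 0.28 to 0.51 with S², 0.24 to 0.39 with S.

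**The case against.** The strongest reply is that this is a notation slip with almost no consequence. S² is how a normal distribution is written in a textbook, and the program may already pass S. No program is available, so the finding concerns the text and not an analysis that has been run. SAP section 8 has two programmers work independently. Few values will be missing, and if no BMI is missing the effect is zero. Step 5 shows a shift that is small against the standard error and without meaningful bias, and most of the deviation from the complete-data result remains after the correction. The study has no powered hypothesis, so no pass-or-fail decision turns on it. Finally, specific sections of a SAP naturally override a general line such as 7.3.

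Most of this stands as a limit on size. It does not remove the error. The SAP prescribes code with a seed, and two programmers who both follow it will agree with each other and be wrong together; if one silently corrects it, the outputs differ or depart from the plan. The point on 7.3 also stands: that part is a wording clean-up and would not merit raising alone.

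**Conclusion.** The concern holds. As written, the call uses the variance where the software expects a standard deviation, and about one third to two thirds of imputed BMI values would be set to the observed extreme, against under 2% with S. This rests on assumed BMI SDs of 4 to 6 and assumed or simulated ranges.

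The effect on the 3-month estimate is probably small: about 1 to 7 subjects given an extreme value if 1 to 5% of 216 lack BMI, and a typical shift of 0.1 to 0.2 mmHg. One further assumption matters. Both documents define the ITT population as all enrolled subjects, enrolment is at consent, and about 350 are to be enrolled to treat about 50. The figures here take the propensity pool to be treated subjects. If screen failures without a baseline were carried into the imputation step, the blood pressure covariates would also be affected and the error would matter far more. That is unlikely to be intended, but the text does not exclude it.

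This should be corrected because the rule is definitely wrong as written and the correction is trivial, not because the result is in danger.

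**What to change.** In SAP 7.7.2.1, write the call as RAND('NORMAL', MU, S), keep the definition of S as the sample SD, and confirm that the analysis program does the same.

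In SAP 7.3, say that missing data are not imputed except for LOCF in escape subjects (7.1.3.1), propensity score covariates (7.7.2.1) and partial dates (Appendix I).

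The cost is one character in the SAP and in the code, plus one sentence. Data collection and sample size are unaffected.
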